13 ASSESSMENT AND DATA COLLECTION

Participating sites will be expected to maintain a file of essential trial documentation (Investigator Site File, ISF). Sites will keep copies of completed CRFs for the trial, or a file note to their location, within the ISF.

13.1 General CRF completion guidance

Investigations in this trial will use the results of local assessments. Data will be collected using paper case report forms (CRFs). CRFs must only be completed by personnel authorised to do so by the Principal Investigator, as recorded on the trial-specific Authorised Personnel Log. The original 'wet ink' version of the completed CRFs should be returned to the Research Fellow at SJUH at the address given in the Investigator Site File.

It is the responsibility of staff at participating sites to obliterate all personal identifiable data on any hospital reports, letters, etc, prior to sending to SJUH. Such records should only include Trial Number, initials and date of birth to identify the participant. The exception to this is the participant consent form, where the participant name and signature must not be obliterated. If signed consent forms are posted to SJUH, they must be sent in a separate envelope and not accompanied by any CRFs containing clinical data.

13.2 Pre-operative assessments and data collection

Preoperatively, patients will be assessed for inclusion into the study according to the criteria given in Section 9 and at the time of outpatient review. General assessment regarding cancer treatment and fitness for surgery will be as per institutional protocol.

Written informed consent must be obtained prior to the commencement of trialspecific assessments.

13.3 Radiological assessment

A specific baseline radiological CRF will be completed with details from the baseline screening CT.

13.4 Operative assessments and data collection

An operative CRF will be completed. This will collate data relating to the operation including:

Surgeon

ASA status

Details of D-Light 5-ALA lymph node assessment

Settings of Storz D-light laparoscopic system for 5-ALA fluorescence detection Type of operation performed

Whether outcome of operation curative, palliative or unresectable in the opinion of the surgeon at the time of operation

Type of anastomosis

Any intra-operative complications, including open conversion

As patients will be undergoing cancer operations, it will not be possible to blind the surgeon to the result of the preoperative CT scan. The preoperative CT scan is fundamental to selection of the patient for curative surgery.

13.5 Pathology Assessment

Histopathological analysis of the colonic resection specimens will be carried out according to internationally agreed criteria (39). Further details are provided in Appendix 3.

This will include:

Fresh specimen photographs Formalin-fixed specimen photographs Cross-sectional slice photographs

Specimen sketch with lymph node mapping

- Number and size of detectable metastatic lymph nodes
- Estimated position of lymph nodes (D1/D2/D3) marked on diagram, using Japanese sub-group classification of lymph node stations

Final histopathology report with full histopathological staging data

Central review of specimens will require a complete set of glass H&E slides (either originals or an extra set) and all of the lymph node blocks and 2 blocks from the tumour. Further lymph node levels will be subjected to immunohistochemical analysis to confirm lymph node status and detect missed metastasis.

As a quality assurance measure, copies of all histopathology reports will be submitted to SJUH. All personal identifiable information must be obliterated from reports prior to sending to SJUH. However, the following patient information should be clearly marked on all histopathology reports to enable tracking and processing:

- Unique trial number (with site number obscured)
- Initials
- Date of birth
- Histopathology report number

As an optional item on the consent form, patients will be asked for consent to obtain their redundant tumour samples from the pathology laboratories in order to subject them to tissue microarray analysis. Research staff from SJUH will request the fixed tumour block from the Dublin centre pathologist in order to maintain confidentiality. On receipt, the sample will be anonymised and securely stored in a Human Tissue Authority (HTA, UK) licensed facility at St James's University Hospital, Leeds. These slides/tissue blocks will be identified by the patient's unique trial number, date of birth, and initials.

13.6 Post-operative Assessment and Data Collection

Post-operative care will be in line with nationally agreed guidance. (e.g. every 30 minutes for the next two hours, and hourly for a 12 hour period thereafter). Following this in the first 2 post-operative days observations will be Routine observations (temperature, pulse, oxygen saturation, blood pressure, and early warning score) will be performed most frequent initially (e.g. every 15 minutes for the first hour), becoming less frequent over time performed 4 hourly. After this period if a patient in considered stable with normal physiological parameters observations will be performed 4 times daily. The frequency and exact content of the assessment will be tailored to the individual patient.

Routine blood tests including Urea and Electrolytes and Liver Function Tests will be performed on a daily basis for 5 days post-operatively.

A single follow-up visit to the outpatient clinic at 30 days postoperative (or review in hospital if still an in-patient) will complete patient involvement in the study. Data collected at this visit will include:

Post-operative complications to 30 days and severity

Adverse events related to colorimetric dye / 5-ALA administration

There will be no trial follow up after 30 days post-operative and no data will be collected beyond this point.

13.7 Follow up after 30-day discharge from the study

After 30 days patients will undergo standard follow up for their colon cancer as per institutional guideline – involvement in the study will not change this standard practice. Data from these investigations and review will not be collected.

13.8 End of Trial

The 'end of trial' for the purposes of the European Clinical Trials Directive will be defined as the last recruited patient's last data collection visit. At this point, the 'end of trial notification' will be submitted to the relevant regulatory authorities (e.g. UK MHRA) and ethics committees.

14 SAFETY REPORTING

Safety will be assessed by review of adverse events from the time of registration into trial to 30 days post-operatively, whether due to IMP administration or intra- and post-operative complications and mortality.

Collection of this data will be via the Case Report Forms and may require expedited reporting depending on seriousness of event.

14.1 General Definitions

Adverse Events (AE)

Any untoward medical occurrence in a patient or clinical trial subject administered a medicinal product and which does not necessarily have a causal relationship with this treatment.

Adverse Reactions (AR)

All untoward and unintended responses to an investigational medicinal product related to any dose administered. This definition implies a reasonable possibility of a causal relationship which is supported by facts, evidence or arguments to suggest a causal relationship. This definition includes medication errors and uses outside what is foreseen in the protocol (i.e. if an AR occurs as a result of a medication error).

Serious Adverse Events (SAE)

Any untoward medical occurrence or effect that:

- results in death,

- is life-threatening
- requires hospitalisation or prolongation of existing hospitalisation,
- results in persistent or significant disability or incapacity,
- is a congenital anomaly or birth defect,
- jeopardised the subject or required intervention to prevent one of the above.
- -is otherwise considered medically significant by the Investigator.

Medical and scientific judgement must be exercised in deciding whether an event is serious (see protocol section 14.5 for Responsibilities). These characteristics / consequences must be considered at the time of the event and do not refer to an event which hypothetically may have caused one of the above.

Where an SAE is deemed to have been related to an IMP used within the trial the event is termed as a **Serious Adverse Reaction (SAR)**.

Suspected Unexpected Serious Adverse Reactions (SUSAR)

An adverse reaction, the nature and severity of which is not consistent with the applicable product information in the summary of product characteristics. Severity describes the intensity of the event.

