6.5 Risks and benefits

Participants for this study will be selected on the basis that they have a diagnosis of colon cancer that requires surgical resection, and are suitable for segmental colectomy with D3 lymphadenectomy. There will be the normal risk of surgical complications associated with general anaesthesia and surgical resection. There is a small risk of photosensitivity reactions related to 5-ALA administration. This includes transient derangement of liver function tests (returning to baseline at 24 – 72 hours post-administration) and skin hypersensitivity reactions due to exposure to UV-light. Other mild and transient side effects associated with 5-ALA administration include nausea, vomiting, tachycardia, and hypotension. When 5-ALA is administered in conjunction with surgical resection of malignant brain tumours, a potential side effect is brain oedema. In response to these potential adverse effects, all patients will be kept out of direct sunlight for at least the first 48 hours following

surgery and monitored for changes in vital signs and liver function (this is normal postoperative care). During the operation patient's eyes and skin will be protected from the operating lights, using standard methods such as sterile drapes and tape to keep their eyes closed.

The above risks to patients will be offset by the advantages arising from taking part in the study. These include potential benefits arising from laparoscopic surgery that is of high quality and scrutinized by pathological assessment, high calibre histopathological analysis of the resection specimen and in particular the lymph node status, and close monitoring during the postoperative period.

The main beneficiaries, should 5-ALA fluorescence diagnosis prove to be effective, will be future generations of colon cancer sufferers. The ability to accurately tailor the radicality of surgery to the stage of the primary cancer should enable optimal oncological resection whilst minimizing the risk of unnecessary postoperative morbidity.

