14.3 Operational Definition and Reporting SAEs/SARs and SUSARs

All SAEs, SARs and SUSARs occurring from the time of registration until 30 days post-operatively must be recorded on the relevant form and faxed to the CTRU within 24 hours of the research staff becoming aware of the event. Once all resulting queries have been resolved, the original form should also be posted to the Research Fellow at SJUH and a copy to be retained on site.

For each SAE, SAR, and SUSAR the following information will be collected:

- full details in medical terms and case description
- event duration (start and end dates, if applicable)
- action taken
- outcome
- seriousness criteria
- causality (i.e. relatedness to trial drug / investigation), in the opinion of the investigator)*
- whether the event would be considered expected or unexpected .

*Assessment of causality and preliminary expectedness must be made by a doctor. If a doctor is unavailable, initial reports without causality and expectedness assessment should be submitted to CTRU within 24 hours, but must be followed up by medical assessment as soon as possible thereafter.

Any change of condition or other follow-up information should be faxed to the CTRU as soon as it is available or at least within 24 hours of the information becoming available. Events will be followed up until the event has resolved or a final outcome has been reached.

All SAEs assigned as both suspected to be related to IMP-treatment and unexpected will be classified as SUSARs and will be subject to expedited reporting to the Medicines and Healthcare products Regulatory Authority (MHRA) and Irish Medicines Board (IMB). The CTRU will inform the MHRA, IMB the main REC and the Sponsor of SUSARs within the required expedited reporting timescales.

Please ensure that each event is reported separately and not combined on one SAE form.

Events not classed as SAEs

The following events will not be recorded as SAEs within this trial:

Hospitalisation for:

- Routine treatment or monitoring of the studied indication not associated with any deterioration in condition.
- Treatment that was elective or pre-planned, for a pre-existing condition not associated with any deterioration in condition.
- Admission to hospital or other institution for general care not associated with any deterioration in condition.

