- Treatment on an emergency, outpatient basis for an event not fulfilling any of the definitions for serious as given above and not resulting in hospital admission.
- Disease progression

Expected AEs

The following events **will be** classed as expected surgical AEs. Any such events meeting the seriousness criteria should be reported as SAEs but will not be reportable as SUSARs unless the Investigator considers the severity to be unexpected:

Operative

- Damage to organ/structure e.g.
 - o Bowel
 - o Bladder/ureter
 - o Major vessel
 - o Nerves
- Faecal contamination
- Haemorrhage
- Surgical emphysema
- Failure of surgical equipment (laparoscopic equipment)

Post-operative

- Altered bowel habit
- Anastomotic leak
- Gastrointestinal fistula
- Gastrointestinal ischaemia/necrosis
- Gastrointestinal obstruction
- Gastrointestinal perforation

- Gastrointestinal stricture/stenosis
- Gastrointestinal ulceration
- Haemorrhage
- Hernia
- Ileus
- Intra-abdominal/pelvic abscess
- Post-operative peritonitis
- Sexual dysfunction
- Stoma prolapse/necrosis
- Urinary dysfunction
- Urinary retention
- Wound infection
- Wound dehiscence

Cardiorespiratory

(May be operative or post-operative)

- Respiratory, including
 - o Acute respiratory distress syndrome/respiratory failure
 - o Aspiration
 - o Atelectasis
 - o Bronchospasm
 - Pleural effusion
 - o Pneumonia/chest infection
 - Pulmonary embolus (or DVT)
- Cardiac, including
 - o Arrhythmia
 - Cardiac failure
 - o Ischaemic heart disease/ myocardial infarction
- Cardio-respiratory arrest

Other

- Acute renal failure
- Back pain
- Cerebrovascular attack/stroke
- Disseminated intravascular coagulation
- Distal limb ischaemia/compartment syndrome
- Metabolic acidosis
- Necrotising fasciitis
- Pressure sore
- Pseudomembranous colitis
- Scrotal swelling
- Sepsis
- Subcutaneous emphysema
- Urinary tract infection
- Delerium

Fax Number for reporting SAE/SARs and SUSARs: [name]

14.4 **Pregnancies and Suspected Pregnancies**

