14.5 Responsibilities

Principal Investigator (PI):

- 1 Checking for AEs and ARs when participants attend for treatment / follow-up.
- 2 Using medical judgement in assigning seriousness, causality and preliminary expectedness using the Reference Safety Information approved for the trial.
- 3 Ensuring that all SAEs and SARs (including SUSARs) are recorded and reported to the CTRU within 24 hours of becoming aware of the event and provide further follow-up information as soon as available.
- 4 Ensuring that SAEs and SARs (including SUSARs) are chased with CTRU if a record of receipt is not received within 2 working days of initial reporting.

5 Ensuring that AEs and ARs are recorded and reported to the CTRU in line with the requirements of the protocol.

CTRU

- 1 Provide office hours cover for receipt of all initial and follow up SAEs, SARs, and SUSARs. The CTRU will conduct an initial review of the core dataset prior to forwarding to CI/Research Fellow for medical review.
- 2 Expedited reporting of SUSARs to the relevant Competent Authorities (MHRA and Irish Medicines Board [IMB]), Main RECs in UK and Ireland and Sponsor within required timelines.
- 3 Pass all data to the Research Fellow for databasing.

SJUH Research Fellow:

- 1 Central data collection and verification of AEs, ARs, SAEs, SARs and SUSARs according to the trial protocol onto a database.
- 2 Preparing annual progress reports to Main RECs in UK and Ireland and periodic safety reports to TSC and DMEC as appropriate.
- 3 Reporting safety information to the independent oversight committees identified for the trial (Data Monitoring & Ethics Committee (DMEC) and / or Trial Steering Committee (TSC)) according to the Trial Monitoring Plan.
- 4 Preparing standard tables and other relevant information for the DSUR in collaboration with the CI and ensuring timely submission to the MHRA, IMB and Main REC in UK and Ireland.
- 5 Notifying Investigators of SUSARs that occur within the trial.
- 6 Checking for (annually) and notifying PIs of updates to the Reference Safety Information for the trial.
- 7 Reporting safety information to the CI, delegate or independent clinical reviewer for the ongoing assessment of the risk / benefit according to the Trial Monitoring

Plan.

- 8 Reporting events to collaborating pharmaceutical company in accordance with the trial contract.
- 9 Any duties as delegated by the CI

Chief Investigator (CI) / delegate or independent clinical reviewer:

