- 1 Clinical oversight of the safety of patients participating in the trial, including an ongoing review of the risk / benefit.
- 2 Using medical judgement in assigning seriousness, causality and expectedness of SAEs where it has not been possible to obtain local medical assessment.
- 3 Immediate review and determination of expectedness for all events assessed as related to the IMP in the opinion of the local investigator.
- 4 Review of specific SAEs and SARs in accordance with the trial risk assessment and protocol as detailed in the Trial Monitoring Plan.
- 5 Assigning Medical Dictionary for Regulatory Activities (MedDRA) or Body System coding to all SAEs and SARs.
- 6 Preparing the clinical sections and final sign off of the Development Safety Update Report (DSUR).

Trial Steering Committee (TSC):

In accordance with the Trial Terms of Reference for the TSC, periodically reviewing safety data and liaising with the DMEC regarding safety issues.

Data Monitoring & Ethics Committee (DMEC):

In accordance with the Trial Terms of Reference for the DMEC, periodically reviewing unblinded overall safety data to determine patterns and trends of events, or to identify safety issues, which would not be apparent on an individual case basis.

Pharmaceutical company:

- 1 Supply of the Study Drug according to the Drug Transfer Agreement
- 2 Labelling of the Study Drug which with the label provided by the sponsor
- 3 Information of the Principal Investigator on all important new safety information for the Study Drug without delay.
- 4 Information of the Principal Investigator on relevant Quality defects as soon as they are known.

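### The SUSAR definition in section 14.1, read literally, needs both nature and severity to be inconsistent with the product information, so some serious unexpected 5-ALA reactions may be classed as expected and may not be expedited.

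*Protocol*

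**What the plan says.** Section 14.1 (General Definitions) gives the only criterion in the protocol for what makes a drug reaction unexpected: "An adverse reaction, the nature and severity of which is not consistent with the applicable product information in the summary of product characteristics". It adds that "Severity describes the intensity of the event".

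Section 14.3 sets the reporting rule: "All SAEs assigned as both suspected to be related to IMP-treatment and unexpected will be classified as SUSARs". These go on expedited timescales to the MHRA, the Irish Medicines Board, the main ethics committee and the sponsor. For each serious event the form records "whether the event would be considered expected or unexpected", as a single judgement.

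For the listed expected surgical events, section 14.3 says that those meeting a seriousness criterion are reported as SAEs but "will not be reportable as SUSARs unless the Investigator considers the severity to be unexpected".

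Section 14.5 gives the Principal Investigator this task: "Using medical judgement in assigning seriousness, causality and preliminary expectedness using the Reference Safety Information approved for the trial". The Chief Investigator, a delegate or an independent clinical reviewer then has a second task: "Immediate review and determination of expectedness for all events assessed as related to the IMP in the opinion of the local investigator".

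**The concern.** The connective in section 14.1 is *and*. On its plain wording, a reaction is unexpected only if its nature and its severity both depart from the product information. Section 14.3 applies a different test to surgical events, where severity alone can make a listed event reportable. No such sentence is given for reactions to 5-ALA itself, the product that SUSAR reporting is about.

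The protocol already names several kinds of 5-ALA reaction. Section 6.5 says: "Other mild and transient side effects associated with 5-ALA administration include nausea, vomiting, tachycardia, and hypotension". It also names transient liver-test derangement and skin reactions to light. For a serious reaction of a familiar kind, unexpected severity is the natural reason to call it unexpected, and the literal wording does not accept that reason by itself.

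At stake is the route by which regulators, the ethics committees and the other centre learn of such an event. A reaction classed as a SUSAR is expedited, and under section 14.5 investigators are notified. Neither provision covers a serious reaction classed as expected. The trial has two centres in two countries, so two sets of assessors could also read the sentence differently.

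**Working it through.** No arithmetic applies, and the protocol gives no figure to reproduce. The check sets the clauses side by side for a serious event already judged related to 5-ALA.

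**Step 1. Inputs.** The definition (14.1), the reporting rule and the surgical-event clause (14.3), and the assessors and their reference document (14.5).

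**Step 2. The four combinations.**

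| Nature consistent? | Severity consistent? | 14.1, literal *and* | Either element suffices |
|---|---|---|---|
| No | No | SUSAR | SUSAR |
| No | Yes | Not a SUSAR | SUSAR |
| Yes | No | Not a SUSAR | SUSAR |
| Yes | Yes | Not a SUSAR | Not a SUSAR |

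The two readings differ in two of the four rows. Of the three rows with some departure from the product information, the literal reading captures one and the alternative captures all three.

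**Step 3. Does the reporting rule in 14.3 settle it?** It needs a serious event that is related and unexpected, and it sets no joint nature-and-severity condition. If the assessor marks a row-two or row-three event as unexpected, it is expedited. But the rule does not say what unexpected means, so the assessor must go back to 14.1.

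**Step 4. Does the surgical-event clause settle it?** It treats row three as reportable on severity alone, but only for the surgical list. It suggests what the authors meant without extending the rule to 5-ALA reactions.

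**Step 5. Do the two assessments settle it?** They provide two medical judgements. Section 14.5 supplies no criterion to replace the one in 14.1, so both assessors may apply the same literal test.

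**Step 6. Reference document.** Section 14.1 tests against the summary of product characteristics. Section 14.5 tells the Principal Investigator to use the Reference Safety Information approved for the trial. The protocol does not say that the two are the same, so they need to be aligned.

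**The case against.** The best opposing case is that section 14.1 only gives general definitions, while the operative trigger is in 14.3 and carries no joint test. The verb in the definition is singular, so nature and severity can be read as one description that fails if either part fails. The strict reading would also exclude a wholly new kind of serious reaction of ordinary severity, which the authors show no sign of intending. The surgical clause points the same way. In addition, every SAE and SAR goes to the CTRU within 24 hours whatever its expectedness, two assessments follow, and sections 17.1 and 18.1 provide real-time DMEC review of events suspected to be related to 5-ALA.

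Much of this stands, and it rules out two stronger conclusions that a reader might draw.

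- *That a known reaction of unexpected severity is not expedited.* The documents support only that it may not be, because an assessor can mark it unexpected under 14.3.
- *That no nausea, vomiting, tachycardia, hypotension, photosensitivity or liver-test reaction could ever be a SUSAR.* This assumes the content of product information that is not at hand. It also overlooks that a severe event, such as serious liver injury, may reasonably be judged different in nature from a transient laboratory change.

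The absence of the word *serious* from the definition is not a substantive fault either. The entry's heading and the rule in 14.3 supply it, and omitting it could only widen the definition. Nor does the dose plan show that such reactions are likely: under section 8.1 the second cohort may receive a lower or a higher dose, depending on activity in the first.

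What remains is that the only written criterion is open to a reading that under-classifies events, and nothing elsewhere in the protocol closes that reading for 5-ALA reactions. The safeguards lower the chance that an event goes unnoticed. They are not expedited reports to regulators and ethics committees.

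**Conclusion.** The point holds as an ambiguous definition that is inconsistent with other sections and can lead to under-classification. Applied literally, section 14.1 leaves out two kinds of related serious reaction: known type with unexpected severity, and new type with ordinary severity. It does not match the severity-alone rule for surgical events in 14.3, and it names a different reference document from 14.5.

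How many events would be affected cannot be estimated from the protocol. That depends on how assessors read the sentence and on what the product information lists. The conclusion rests on the protocol's wording alone and on no outside regulation. Endpoints, sample size, error rates and progression rules are not affected. It should be corrected because it concerns an operative safety rule and the correction is small.

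**What to change.** Replace the defining sentence in section 14.1 with: *A serious adverse reaction whose nature or severity, either alone being enough, is inconsistent with the trial's approved Reference Safety Information.* This makes explicit that one departure suffices for 5-ALA reactions, agrees with the severity-alone clause and the seriousness condition in 14.3, and uses the reference document named in 14.5. A short cross-reference from the reporting rule in 14.3 to this definition would fix the meaning of unexpected there.

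The cost is one sentence in a protocol amendment and possibly a few more expedited reports. No data collection or analysis changes.
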